# Abstract

## Background

In the next decade, there will be a doubling of older Veterans for whom the VA has a requirement to provide long-term care. The Veteran's Health Administration Office of Geriatrics and Extended Care (GEC) is seeking to preserve Veteran independence in the community through the Veteran-Directed Home and Community-Based Services Program (VD-HCBS). VD-HCBS is a person-centered consumer-directed program that provides Veterans the opportunity to self-direct their long-term services and supports (LTSS) and continue to live independently at home. GEC is planning to expand VD-HCBS to an additional 90 VAMCs over the next 3 years. This project will conduct a mixed-methods evaluation of the Veteran and Caregiver experience with the VD-HCBS program, and identify implementation factors that help facilitate successful program rollout and administration.

# Objectives

This study will 1) examine the Veteran experience with VD-HCBS by analyzing operational data on satisfaction, unmet needs, and quality of life and b) interviewing Veterans to capture the experience in their own words; 2) Understand the effect of VD-HCBS on Caregiver wellbeing through phone surveys aligned with the Caregiver Support Program and 3) improve the process of future VD-HCBS implementation by interviewing VA and ADNA coordinators about the process of implementing the VD-HCBS.

# Methods

There are three primary methods for this proposal request: a secondary analysis of operations data related to VD-HCBS, a telephone survey with VD-HCBS caregivers and semi-structured qualitative interviews with Veterans or Caregivers and VD-HCBS program coordinators. For the secondary data analyses, we will obtain survey data from Veterans through a Data Use Agreement with the VA Office of Geriatrics and Extended Care (GEC). This operational data set is collected through the VD-HCBS program and the VA-CARES program as part of routine care. This data will allow us to conduct analyses on Veteran satisfaction, needs (met and unmet) and quality of life.. A telephone survey will be conducted with VD-HCBS caregivers to understand their experience as a caregiver in the VD-HCBS program. Additionally, qualitative interviews will be conducted with Veterans selected at random regarding their experience with the VD-HCBS program and how the program is meeting their needs. In addition, qualitative interviews will be conducted with VA based and ADNA based coordinators of the VD-HCBS program to gain insight into the implementation of the program and will help identify facilitators and barriers that impact implementation of VD-HCBS for VAMCs and ADNAs.

# Impact

This study will evaluate the impact of the VD-HCBS program and provide key insights into the implementation and effectiveness of this program. This evaluation may provide insight to VA policymakers and VA care providers that helps them ensure that community based LTSS options are adequately administered and help refine policies regarding the mission and operations of VD-HCBS to align with VHA and GEC goals. List of Abbreviations

ACL -- Administration for Community Living

ADNAs -- Aging and Disability Network Agencies

BIC -- Bayesian Information Criterion

CCDE -- Cash and Counseling Demonstration and Evaluation

CDW -- Corporate Data Warehouse

CFIR -- Consolidated Framework for Implementation Research

CITI -- Collaborative IRB Training Initiative

COIN -- Centers of Innovation

CREATE -- Collaborative Research to Enhance and Advance Transformation and Excellence Initiative

ERIC -- Expert Recommendations for Implementing Change

FMS -- Financial Management Service

GEC -- Office of Geriatrics and Extended Care

GLMMs -- Generalized Linear Mixed Models

HSR&D/QUERI -- Health Services Research & Development/Quality Enhancement Research Initiative

IIR -- Investigator Initiated Research

IRB -- Institutional Review Board

LTC -- Long-Term Care

LTSS -- Long-Term Services and Supports

NRCPDS -- National Resource Center for Participant-Directed Services

OIG -- Office of Inspector General

P1a -- High Priority Veteran

PCAFC -- Program of Comprehensive Assistance for Family Caregivers

PEPReC -- Program Evidenced-based Policy Resource Center

QCA -- Qualitative Comparative Analysis

QUAN+QUAL -- Quantitative/Qualitative

SCI -- Spinal Cord Injury

TBI -- Traumatic Brain Injury

USH -- Undersecretary for Health

VA-CARES -- VA Caregiver Evaluation Center

VAMCs -- VA Medical Centers

VD-HCBS -- Veteran-Directed Home and Community Based Services

VHA -- Veterans Health Administration

VINCI -- VA Informatics and Computing Infrastructure

VPN -- Virtual Private Network

## 2.0 Introduction

In the next decade, the number of older high priority (P1a) Veterans will double. The VA has a statutory obligation to purchase or provide institutional care to all P1a Veterans. At a cost of \$110,000 per Veteran per year for institutional care, the ability of the VA system to honor its statutory obligations will be challenged with current resources. As stated by the 2013 Office of the Inspector General report,  there is a rapid need to rebalance the focus from institutional programs to non-institutional programs. In FY14, VA's Office of Geriatrics and Extended Care (GEC) spent 74% of its budget on institutional care and 26% on non-institutional long-term services and supports (LTSS). For comparison, state Medicaid programs, which are under a statutory obligation to provide institutional care, devote the majority (51%) of LTSS spending to non-institutional care. In an effort to meet this impending demand, GEC has been working toward developing a dynamic system of LTSS that shifts the delivery of long-term care (LTC) from institutions to the community.

As part of this rebalancing plan, GEC has implemented many innovative programs to postpone or prevent institutionalization. Recognizing the need to increase home and community-based services (HCBS) utilization for high-need Veterans and following the reported success of the Cash and Counseling Demonstration and Evaluation (CCDE), GEC leadership implemented a

program for Veterans to self-direct their care thereby enabling them to maintain community residence and avoid institutionalization: Veteran-Directed Home and Community Based Services (VD-HCBS). In 2008, a partnership was formed between VA and the Administration for Community Living (ACL) to implement the VD-HCBS program, capitalizing on the home care service delivery experience and skills of ACL's Aging and Disability Network Agencies (ADNAs) and the VHA's commitment and resources. Through this partnership, VAMCs purchase VD-HCBS care management from ADNAs on behalf of Veterans. GEC is planning an expansion of VD-HCBS to an additional 90 VA sites over the next 3 years.

## Description of the VD-HCBS Program.

The research project described in the protocol is an evaluation of the VD-HCBS program. Like the participant-directed programs developed for Medicaid programs (i.e. Money follows the Patient, or Cash and Counseling),  VD-HCBS maximizes Veteran-centered care and independence. VD-HCBS provides Veterans with a monthly financial allotment based on an assessment of the extent of their need for assistance with personal care due to injury or the impact of disease. Veterans have the opportunity to spend their allotment on services that best meet their needs, such as personal care workers whom they hire and manage themselves. Personal care workers may be family members who otherwise may not be able to afford to stay out of the workforce to care for the Veteran. Allotted funds may also be spent on supplies, home modifications, and/or adaptive equipment not available through other VA programs.

ADNAs play a key role in identifying Veteran's needs, coordinating Veteran services, financial reporting, and coordinating with VA. An ADNA coordinator works with the Veteran to 1) develop a person-centered plan for the Veteran's care, 2) identify risks to Veterans' health and safety and include in the plan how Veterans and their caregivers can mitigate those risks, 3) monitor spending and service utilization and 4) provide ongoing options counseling and support to Veterans. In addition, the Veteran (or appointed representative) and the ADNA representative work closely with a Financial Management Service (FMS) to manage employment taxes and insurance and process payroll and timesheets. The ADNA bills the VA for their services and oversight of VD-HCBS recipients.

## **Previous VD-HCBS Evaluations.**

In an evaluation of the VD-HCBS conducted by Boston College's National Resource Center for Participant-Directed Services (NRCPDS), survey responses from VD-HCBS Coordinators at VAMCs indicated that VD-HCBS is filling a niche for Veterans at risk of nursing home placement. The survey results further pointed out that, for many, collaboration between VAMCs and ADNAs has been enhanced by mutual benefit; but in some cases, these partnerships were complicated and difficult. The evaluation report suggests that role clarification and coordination efforts were critical to maximize the roles of the VA and ADNA. In complementary work conducted by investigators at the Providence VAMC Center of Innovation for LTSS (LTSS COIN), the majority of VD-HCBS coordinators at ADNAs interviewed suggest that the experience of collaborating with VAMCs was positive and interviews identified several key mechanisms for facilitating a successful partnership (e.g., including frequent communication, training, designated VAMC staff personnel, and active involvement of the VAMC). Veterans currently enrolled in VD-HCBS who participated in the NRCPDS' qualitative "Voice of Veterans" study called the program "life changing." While the Veterans interviewed said they would recommend VD-HCBS, they also made a number of suggestions to improve the program. Preliminary analysis of these data reveals program implementation issues from the perspective of users, as well as concern about consistency across programs, access for more Veterans, and sustainability of VD-HCBS.

Importance of Caregiving in maintaining Veteran Independence. Because Veterans eligible for VD-HCBS are vulnerable with functional deficits and significant caregiving needs, the caregiver is an indispensable partner in maintaining community independence. The emotional, physical, and financial tolls of informal caregiving are well documented in the civilian and Veteran populations. According to the 2015 National Survey of Caregiving, one in five Caregivers report high levels of physical strain resulting from caregiving, two in five consider caregiving to be emotionally stressful, and about one in five reports experiencing financial strain. Given the relationship between Caregiver burden, stress, and well-being and the ability for the care recipient to remain in the home, the impact of VD-HCBS on Caregivers merits attention. Previous literature has suggested that consumer directed programs like VD-HCBS benefits consumers (see, for example, Tilly, et al.) and Caregivers. Caregiver benefits include decreased worry, physical, and financial strain, along with the ability to enjoy respite time. Focus groups with 23 Caregivers of Veterans enrolled in VD-HCBS were conducted by our partners at NRCPDS as part of their Voices of Veterans study. Analysis of these focus groups revealed major sources of stress and elucidated mechanisms behind stress relief and support experienced in VD-HCBS. For example, participants commented on the program's ability to enable Veterans to remain home, provide stress relief, and afford spousal Caregivers more time with their Veteran loved one spent as a "couple" resulting in reciprocal, mutual benefits. While the Voices of Veterans study was the first to include VD-HCBS Caregivers, there has been no other work, to date, that has specifically evaluated the impact of the VD-HCBS program on Caregivers as measured by improvement in their well-being.

#### SIGNIFICANCE

**Knowledge to be gained.** Proponents of VD-HCBS suggest that expansion of this program could be one promising solution to meet the increased need for LTSS while containing costs and promoting Veteran-centered care. In addition, it provides an innovative approach to HCBS delivery to Veterans living in rural areas or far from VAMCs. Several VAMCs have documented the success of their programs both in terms of Veterans' satisfaction and reduced NH utilization,  However, uptake of the program varies greatly across the country: only 51 VAMCs offer VD-HCBS and the numbers of Veterans enrolled at each site range from one to 100+. There has been no formal evaluation of implementation or effectiveness of the program and therefore the evaluation we are proposing is significant because it will be the first major evaluation of the effect and implementation of the VD-HCBS program.

**Impact on Veterans and the VA.** Veterans enrolled in VD-HCBS represent a vulnerable population, with most having functional or cognitive deficits, needing >20 hours of home care, and meeting eligibility for long term care. At a cost of \$110,000 per Veteran per year for long-

Version 04/23/2018

term care and a doubling of the number of Veterans eligible for VA-paid long-term care, GECs and Veterans have a mutual interest in preserving Veteran independence in the community. As a result, VD-HCBS has tremendous opportunity to improve the fiscal outlook of GEC's LTSS while delivering the highest level of Veteran-centered care. This proposed VD-HCBS evaluation leverages the utilization analysis of PEPReC, by systematically capturing perspectives of Veterans and Caregivers to provide a comprehensive view of the value of VD-HCBS to all stakeholders.

**Alignment with VA Priorities.** VD-HCBS expansion is consistent with the VA and GEC Mission and Vision. Importantly, VD-HCBS highlights the efforts of GEC to rebalance toward home and community-based services (HCBS) as required by the OIG. Access to HCBS is the priority goal of both the VA Secretary and the VA Undersecretary for Health (USH). Because VD-HCBS is built on a participant-directed, patient-centered framework, the program is consistent with improving the Veteran Experience (VA Secretary Priority #1; USH Priority #2). The expansion of VD-HCBS, a best practice in HCBS (USH Priority #3), enhances strategic partnerships (VA Secretary Priority #5 & USH Priority #4) and builds a culture of improvement (VA Secretary Priority #4) in a high performing network (VA USH Priority #4). Evaluation of VD-HCBS aligns with the "MyVA" initiative which is Veteran-centric and objectives to provide access to consistent programs throughout the VHA system.

#### INNOVATION

The large-scale expansion of VD-HCBS presents an unparalleled opportunity to understand and measure change in the VA. In concert with the outcomes of VD-HCBS, our implementation evaluation will provide insight into GEC programs at VAMCs (educating GEC leaders), but also other VACO program offices looking at implementation. With the diverse team assembled and the comprehensive evaluation proposed, we will produce evidence to inform VA program implementation and dissemination, a critical component of the VA's priorities to develop high-performing, highly-reliable, and consistent networks. Through collaborations with GEC, PEPReC, ACL, and NRCPDS, we seek to leverage the investment in VD-HCBS to describe the value of participant-based programming within VA and the nation. The findings from this study will have implications for future VA-Community partnerships, and can be informative for the organizations providing this contracting service as well as for the providers enrolling in the network.

The individual components of our evaluation are innovative. Large scale measurement of Veteran independence, unmet needs, and satisfaction of a large program is unique in the VA. Additionally, including mixed methods will allow a comprehensive understanding of how Veterans are impacted by VD-HCBS. The inclusion of the Caregiver survey results will provide a first look at how this program may enable Veterans to remain in their homes through improving Caregiver well-being.

#### 3.0 Objectives

In this evaluation, we will test the impact of the VD-HCBS program on Veterans and their Caregivers while simultaneously gathering information on its delivery and implementation.

# Specific Objectives:

**Objective 1**: To describe the impact of VD-HCBS on Veterans' satisfaction, unmet need for services, quality of life, and independence. Using mixed methods, this objective will provide a comprehensive view of the value of the VD-HCBS program to vulnerable Veterans and create a model system for describing the value of GEC programs.

Hypothesis: Our working hypothesis is that Veterans participating in the VD-HCBS program will experience improvements in satisfaction, unmet need for services, quality of life, and feelings of independence compared to before their participation in the program.

**Objective 2:** To understand the effect of VD-HCBS on Caregivers' well-being. As Veterans lose function, Caregivers are critical to community living. We will conduct a telephone survey with VD-HCBS cargivers to compare Caregivers' financial strain, depressive symptoms, caregiving stress, health status, and positive caregiver experiences to a propensity matched population to determine the impact of the VD-HCBS program on Caregivers.

Hypothesis: Our working hypothesis is that Caregivers of Veterans participating in VD-HCBS will experience reductions in financial strain, depressive symptoms and caregiving stress, and overall improvements in their health and caregiver experiences.

**Objective 3:** To examine the implementation of the VD-HCBS program expansion. VD-HCBS is a complex program in a complex VAMC environment. Utilizing constructs from the Consolidated Framework for Implementation Research (CFIR) and a published typology from the Expert Recommendations for Implementing Change (ERIC) project, we will interview VA and ADNA VD-HCBS coordinators to systematically identify common contextual factors and implementation strategies.

This proposed VD-HCBS evaluation leverages the information that will be obtained by GEC in this expansion by systematically capturing perspectives of Veterans and Caregivers to provide a comprehensive view of the value of VD-HCBS. Additionally, the large-scale expansion of VD-HCBS presents an unparalleled opportunity to understand and measure change in the VA. In concert with the outcomes of VD-HCBS, our implementation evaluation will be critical to determining how the program was executed. With the diverse team assembled and the comprehensive evaluation proposed, we will produce evidence to inform VA program implementation and dissemination, a critical component of the VA's priorities to develop highperforming, highly-reliable, and consistent networks. Through collaborations with our

Version 04/23/2018

operation partners we seek to leverage the investment in VD-HCBS to describe the value of participant-based programming within VA and the nation.

#### **Data Use Agreements:**

Version 04/23/2018

For this analysis, we will enter into three data use agreements in order to complete our secondary data analysis aims. We will enter into a Data Use Agreement with the Office of GEC for the use of the ADNA assessments and The Lewin Group readiness assessments both of which are reported to GEC as part of routine care/service. Only the ADNA Assessments contain PHI. The second data use agreement will be with the VA Caregiver Support Program. The caregiver survey data will be used as a comparison group for our research analysis of the Caregiver Survey (Objective 2). Finally, we will enter into a data use agreement with PEPReC for the VD-HCBS program analysis data including VAMC randomization criteria, the utilization outcomes analysis, and the economic outcomes analysis data. This will allow us understand the context of implementation in programs that are 'successful' in implementation and outcomes development of VD-HCBS.

# **5.0 Study Procedures**

## Objective 1 –

The purpose of Objective 1 is to understand the impact of the VD-HCBS program on similar outcomes for Veterans using a mixed qualitative and quantitative method design. The quantitative methodology (Objective 1a) will be a secondary data analysis of the ADNA assessments. These data will be obtained via a Data Use Agreement (DUA) with the VHA Office of Geriatrics and Extended Care. These assessments contain surveys that are administered at each Veteran's initial in-home visit, and quarterly thereafter as part of the national roll-out and operation of the VD-HCBS program. PHI is included in this data set including name, social security number, and date of birth., address, phone number, email (if available), and caregiver contact information. All secondary survey data will be stored on the restricted access Providence VA research server, in a restricted folder in accordance with VA policy.

For the qualitative aim (Objective 1b), we will be conducting semi-structured telephone interviews with a random sample of Veterans (n=64) newly enrolled to VD HCBS (to include the sites involved in the roll out and all other sites with VD HCBS) to gain further insight into the ways in which the VD-HCBS program has impacted their lives. Veterans will be interviewed at two time points in 12 months after initiation of VD-HCBS, for a total of 128 interviews. If a Veteran is unable to communicate on the telephone, we will instead contact their caregiver and invite them to share their own experiences with the program. These interviews will be recorded for transcription purposes. Participants will be sent an information consent sheet, however consent for the interviews and the recording will be acquired verbally as detailed in the interviews will be coded as described in the data analysis section.

## Recruitment Methods:

All quantitative data will be obtained from the data owners (VHA Office of GEC), following an approved Data Use Agreement in accordance with VHA policy. As

part of standard operations, the ADNA meets with the Veteran initially and every 90 days thereafter. During these meetings it is customary for the ADNA to ask about current services, as well as, unmet needs and satisfaction with the program.

The VD-HCBS program currently enrolls ~825 new Veterans annually at existing sites. At newly opened sites, there is a period between readiness review and enrolling Veterans that delays early recruitment. As a result, we anticipate that ~825 Veterans among the new sites will be enrolled annually. With 4 routine ADNA assessments per Veteran, we expect to receive up to 6,600 surveys.

A total of 64 respondents consisting of Veterans or Caregivers will be recruited for qualitative portion of this objective. Recruitment packets will initially be sent using via US Mail to the Veterans' listed residences in the ADNA assessment data or should the addresses not be listed, by using the listed SSN in the ADNA assessment data to access the national Electronic Health Record (EHR) by way of CAPRI/VistAWeb and/or JLV. We will randomly select four Veterans enrolled in VD-HCBS from each of the 16 VAMCs chosen for the implementation analysis described in Objective 3. Veteran selection will be done by inputting all case numbers at a VAMC into a random number generator. This packet will include an introduction letter, refusal postcard, and the CIRB approved information consent sheet. The letter will inform potential participants about the interview, the goal of the interviews, that the interviews will be recorded for transcription purposes and will provide contact information for a Providence-based project staff member to address any questions or concerns they may have prior to participating. They may also use this telephone number to indicate their refusal to participate.

The CIRB approved information consent sheet for Veterans to keep, will describe the procedures and risks and contain contact information should they have any questions.

Also included will be the refusal to participate postcard. Veterans will be asked to complete and return this postcard if they do not wish to participate in the study. Receipt of this postcard by the project staff will terminate all future contact with the Veteran regarding this project.

For Veterans whom we do not receive a refusal postcard or telephone call, we make no more than three attempts to contact them via telephone between the hours of 10am and 7pm, in their representative time zones.

If it is discovered during these attempts that the Veteran is unable to participate due to medical limitations such as being non-verbal, aphasic, or cognitively impaired, the project team will exclude the Veteran from participation and instead will contact the Veteran's Caregiver as listed in the ADNA survey. At this point, a packet including the introduction letter, refusal postcard, and the CIRB approved Caregiver information consent sheet will be sent to the named caregiver. Receipt of this postcard by the project staff will terminate all future contact with the Caregiver regarding this project.

For Caregivers whom we do not receive a refusal postcard or telephone call, we make no more than three attempts to contact them via telephone at the number listed in the ADNA survey between the hours of 10am and 7pm, in their representative time zones.

If the caregiver agrees to participate in this project, the caregiver will be asked questions regarding their own experiences with the program as described in the Caregivers interview guide and this data will be analyzed separately.

In order to ensure that the appropriate number of Veterans and Caregivers are enrolled, for every instance where we receive a refusal or are unable to make contact with the Veteran or Caregiver, a new Veteran will be randomly selected and the recruitment process will repeat.

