## 7.0 Data Analysis

#### **Objective 1:**

Quantitative Analysis of Veteran Survey Data - We will analyze the quantitative data from the Veteran Assessment survey data by calculating descriptive statistics and means for the survey items. We will compare the responses at baseline to responses at 3 months, and to responses at 12 months to gauge early and long-term change in the various domains. We will also calculate differences in change by Veteran characteristics, including care arrangement, functional impairment, socioeconomics, and demographics. This descriptive pre-post analysis will provide a first look at the impact of the VD-HCBS program on Veterans. Lastly, we will use finite mixture models to identify subgroups of Veterans that have similar trends in outcomes. Finite mixture models are clustering methods based upon a statistical model with stochastic elements. Formally, they can be written as  $p(Y_i) =$  $\sum_{i=1}^{J} \pi_i F(Y|G_i = j)$ , where Yi is a vector of outcomes for Veteran i,  $\pi_j$  is the proportion of subgroups j among Veterans, Gi is an unknown group classification for Veteran i, F is the distribution of the outcome at the that subpopulation, and J are the number of subpopulations. We will examine different possible values for the number of subgroups, and select the number with the highest Bayesian Information Criterion (BIC). Our initial model for F will be multivariate Gaussian distribution, which may require appropriate transformations of some of the outcomes (e.g., log). If the Gaussian model will not provide a good fit for the data, we will examine other possible models such as a mixture of t distributions, or a mixture of skewed-Normal distributions. After the model identifies the possible subgroups, we will attempt to describe them by examining the trends in the observed outcomes (e.g., Veterans with increasing outcome trends overall, patients with moderately increasing outcomes at 3 weeks but stable at 12 months). These subgroups will enable us to identify the possible patterns that exist among Veterans exposed to the VD-HCBS program. Following this identification, we will examine qualitative (see below) or quantitative variables that are possibly associated with these patterns, so that we could provide further understanding on the possible effectiveness of the program.

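### As the plan describes it, the Veteran satisfaction item concerns the program and has no meaningful baseline at the initial visit, so baseline contrasts should be limited to items with the same wording and referent at every wave

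*Combined protocol and SAP*

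**What the plan says.** The hypothesis under Objective 1 (Section 3.0, Specific Objectives) is that "Veterans participating in the VD-HCBS program will experience improvements in satisfaction, unmet need for services, quality of life, and feelings of independence", and the reference point is the period before enrollment: "feelings of independence compared to before their participation in the program".

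The quantitative data are the ADNA assessments. Section 5.0, Objective 1 describes them as containing "surveys that are administered at each Veteran's initial in-home visit, and quarterly thereafter". Recruitment Methods in the same section says that "the ADNA meets with the Veteran initially and every 90 days thereafter", and that the ADNA customarily asks at these meetings about current services, "unmet needs and satisfaction with the program".

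Section 7.0, Objective 1 sets the contrast: "We will compare the responses at baseline to responses at 3 months, and to responses at 12 months". It characterizes the result this way: "This descriptive pre-post analysis will provide a first look at the impact of the VD-HCBS program on Veterans".

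**The concern.** A before-and-after difference is interpretable only if the same quantity is measured on both occasions. The one description of the satisfaction question ties it to the program, and the first measurement comes at the initial home visit. The program description in Section 2.0 has the ADNA coordinator building the care plan with the Veteran, and the Veteran hiring and managing workers. Services can hardly have been experienced when the first assessment is completed. A rating of the program at that point would be blank, an expectation, or an answer about something else.

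Satisfaction is the first outcome named in the Objective 1 hypothesis. Section 7.0 presents the pre-post comparison as a view of program impact, and it contains no rule on item wording, on keeping the referent constant, or on baseline answers that do not apply. If a difference were computed anyway, it could be reported as improvement due to VD-HCBS when it reflects only that the first answer meant something different from the later ones.

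**Working it through.** This is a question of measurement, so no power or sample-size formula applies. The plan gives no alpha, effect size or standard deviation for the quantitative part of Objective 1.

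**Setting the statements side by side**

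1. Target (Section 3.0): change in satisfaction relative to before participation.
2. Contrast (Section 7.0): baseline against 3 months and against 12 months.
3. Baseline (Section 5.0, Objective 1): the survey at the initial in-home visit.
4. Object of the question (Section 5.0, Recruitment Methods): the program. Current services and unmet needs are listed there as separate topics, so satisfaction with current services is not the natural reading of the sentence. The abstract's Objectives likewise place satisfaction within the Veteran's experience of VD-HCBS.
5. Other sources: the text describes no retrospective item, no separate pre-program satisfaction measure and no comparison group for this analysis.

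**What follows under each possible wording**

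- *The item asks about the program at every wave.* The first value is missing or is not a rating of experienced service. Neither baseline contrast estimates the hypothesized improvement. The 3-month and 12-month levels, and the change between them, remain meaningful.
- *The item asks in the same words, at every wave, about the care the Veteran currently receives.* The referent is constant and only the care has changed. Baseline against 3 and 12 months is then the contrast the hypothesis calls for, and it is valid.
- *The first survey is worded about earlier care and later ones about VD-HCBS.* Two different questions are being compared, and the difference mixes a change of question with any change in satisfaction.

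The description in Recruitment Methods matches the first case. The instrument is not reproduced, so the second and third cannot be excluded.

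**Scale, from the plan's own counts**

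- Inputs (Section 5.0, Recruitment Methods): about 825 new Veterans a year at existing sites, about 825 at new sites, 4 assessments each.
- Plan's total reproduced: (825 + 825) × 4 = 1,650 × 4 = 6,600, as stated.
- Initial-visit surveys, counting the initial visit as one of the four: 1,650, and 1,650 / 6,600 = 25%. These are the whole baseline side of the contrast.
- Later surveys: 6,600 − 1,650 = 4,950. These can still describe satisfaction after enrollment.

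These are upper limits, since the plan expects up to 6,600. On the same counting, 90-day spacing places the four visits at about 0, 3, 6 and 9 months. A 12-month value would be a fifth visit, or 1,650 × 5 = 8,250 surveys in all. That is a separate matter, but the 12-month comparison already in Section 7.0 depends on it.

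**The case against.** The strongest reply is that a sentence about routine practice is being read as if it were a survey item. It sits under recruitment, says what is customary, and covers the first and later meetings together without saying that every topic is raised in the same form at each. The hypothesis and the analysis section speak of satisfaction with no object. Part of the protocol between Section 3.0 and the Data Use Agreements subsection was not available for this review, which weakens any argument from silence. The analysis is descriptive, no confirmatory test depends on it, and interviews at two time points also address Veterans' experience. Striking satisfaction from the hypothesis without seeing the item could throw away a good baseline.

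Most of this stands, and it limits the point in three ways. A reader might infer:

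- *That improvement in satisfaction cannot be estimated at all.* The documents do not support this. A same-worded item on current care would make the contrast valid, and the wording is not shown.
- *That the Qualitative Comparative Analysis outcome under Objective 3 is compromised.* That outcome is a satisfaction level recoded as present or absent, not a change from baseline. An empty baseline would not by itself affect it.
- *That the finite mixture model is distorted.* Section 7.0 refers to a vector of outcomes without naming satisfaction as a member.

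The reply does not remove the core. The plan's only statement of what the question concerns points to the program, and Section 7.0 would apply the baseline contrast to it without any safeguard. A descriptive analysis offered as a look at impact can still mislead if its first value means something else.

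**Conclusion.** The point holds conditionally. With the satisfaction question as the plan describes it, the comparison with the period before participation has no meaningful baseline, and the baseline-to-3-month and baseline-to-12-month differences would not measure improvement in a single quantity.

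Its reach is one of the four Objective 1 outcomes. Unmet need, quality of life and independence can have a meaningful value at the first visit and are not questioned. The direction and size of any error cannot be given without item wording and score distributions.

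The conclusion assumes that the sentence in Recruitment Methods reflects the item actually used, and that the initial visit precedes any real experience of services. If the instrument shows a current-care item worded identically throughout, the contrast for that item is sound.

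**What to change.** In Section 7.0, Objective 1, state each satisfaction item and what it refers to at each wave, then add a rule:

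- Limit comparisons with baseline to items whose wording and referent are identical at every wave. Apply the same limit to any baseline values entered in the mixture model.
- Keep the pre-post contrast for any satisfaction item that meets this condition.
- For an item about satisfaction with the program, report levels at 3 and 12 months and the change from 3 to 12 months. Do not count it as evidence for the hypothesis of improvement over the pre-program period, and say so beside the hypothesis in Section 3.0.

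The cost is a few sentences in two sections, with no new data collection. The later surveys, up to 4,950 on the plan's counts, remain usable. The price is that no before-and-after claim can be made for program-specific satisfaction.
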